#### **F. Risk/benefit assessment:**

*Blood draw.* This risk is very minimal. However, certain risks including discomfort, blood clot, minor bleeding, bruising, infection, and redness can occur. Aseptic techniques will be used to minimize such risks.

*Fitness testing.* Some risks are associated with the exercise testing used to assess maximal aerobic capacity. Maximal cardiorespiratory fitness testing is safe in elderly participants[4, 5, 22], but adverse events are possible . Because risks could be serious, initial screening by maximal stress test will be performed in a clinical setting under the direction of a physician. Muscle soreness and strain are possible with exercise testing, but these are not a serious risk. The maximal aerobic capacity test represents greater risk of cardiovascular events than the acute exercise stimulus because of the increased intensity of the exercise. However, events are extremely rare, and participants will be screened for risk of cardiovascular disease and symptoms. Emergency equipment, including defibrillator, and ambulance plan are available for all participants.

*Genotype.* APOE e4 genotype data will be requested from the KU ADC (HSC #11132) for subjects who participate in the KU ADC clinical cohort and will be generated from all other participants. There is potential negative impact if this information were to become known. Thus, this information will be stored electronically in a secure password protected RedCAP database and any paper copies of records will be filed by number in accordance with professional standards of privileged information in a secure badge-access file room at the KU CRC.

*PET/CT Risks.* PET/CT scans include exposure to radiation. This radiation exposure is not needed for your medical care. The amount of radiation you receive annually in this study is about the same amount that you receive in 166 months (14 years) from background radiation. The long-term effect of concern from exposure to radiation is an increase in the risk of getting cancer. Most cancers caused by radiation develop

20 or more years after the exposure to radiation.

### **Adequacy of Protection Against Risk**

**Protection Against Risk:** All research data are maintained confidentially by numerical code in password-protected databases. All paper copies are filed by number in accordance with professional standards of privileged information. Confidentiality is strictly safeguarded by HIPAA-compliant standards. Protected health information is not divulged to any outside party or the subject's personal physician unless requested in writing by the subject after full disclosure of risks related to divulging protected health information. To minimize venipuncture-related discomfort, an experienced nurse clinician performs venipuncture. Maximal exercise testing will be performed in the KU CTSU with the supervision of a medical monitor. A clinician will also be available for the exercise sessions at KUCC-OP.

### **Potential Benefits of the Proposed Research to the Subjects and Others**

The mechanisms that underly exercise-mediated improvement in cognition are not well understood, but may involve peripherally-released factors that are best detected acutely following exercise. Repeated, transient increases in certain biomarkers in response to exercise - the "acute exercise response" could over time provide physiological benefit. Moreover, identifying specific acute effects of exercise on the brain (i.e. changes in cerebral glucose metabolism) may help to quickly identify training modalities/intensities that are most likely to elicit long-term benefit.

#### **G. Location where study will be performed:**

**Performance sites:** Visit 1: KU Medical Center Clinical Research Center (CRC) Clinical and Translational Science Unit (CTSU). Visits 2 and 3: KU Cancer Center Overland Park (KUCC-OP). Visit 4: KU Medical Center, Hoglund Brain Imaging Center (HBIC). Study records will be kept at the KU CRC.

#### **H. Personnel who will conduct the study, including:**

1. Indicate, by title, who will be present during study procedure(s):

Visit 1: CTSU Exercise Physiologist, Study Coordinator, CTSU Medical Monitor. Visits 2 and 3: KUCC-OP Radiology staff and nurse, PI, Study Coordinator, Visit 4: HBIC MRI Technician

2. Primary responsibility for the following activities, for example:

- Determining eligibility: Study Coordinator
- Obtaining informed consent: Study Coordinator
- Providing on-going information to the study sponsor and the IRB: PI
- Maintaining participant's research records: Study Coordinator
- Completing physical examination: CTSU nurse
- Taking vital signs, height, weight: CTSU nurse
- Drawing / collecting laboratory specimens: CTSU nurse, KUCC-OP nurse, PI and study coordinator
- Performing / conducting tests, procedures, interventions, questionnaires: Exercise Physiologist, CTSU nurse, PI, study coordinator
- Completing study data forms: Study Coordinator
- Managing study database: PI, Study Coordinator

## **I. Assessment of Subject Safety and Development of a Data and Safety Monitoring Plan**

Study personnel and/or nursing staff will continually monitor participants for adverse events.

Cardiorespiratory fitness testing will be scheduled when a CTSU safety monitor is available. In accordance to the Data Safety Monitoring Plan (DMSP), there will be Data Safety Monitoring Committee (DSMC) assigned to evaluate safety concerns quarterly. A report will be provided to the DSMC with enrollment, adverse event, and protocol deviations. All serious adverse events will be reported to safety DSMC within 48 hours. The PI and other study staff will be examining research data on a subject to subject basis to ensure that it is accurate and to address any problems that may arise with the protocol. In addition [name] will meet at least once per month to discuss data collection and any issues that may arise.

**Plan for Adverse Event Reporting:** Adverse events will be defined as any untoward medical occurrence in study participants or others immediately involved in the performance of the protocol, which does not necessarily have a causal relationship with the study treatment, but results in a change in intervention, daily function, hospitalization or rated category 3 or above using the National Cancer Institute Common Terminology Criteria for Adverse Events (CTCAE) v3.0. Expected events such as minor bruising following the blood draw will not be considered an AE. Staff will continually monitor participants for adverse events throughout each study visit and reported to the DSMC on a semi-annual basis

## **III. Subject Participation**

### **A. Recruitment:**

The KU ADC has an excellent history of recruitment. We will leverage the KU ADC Outreach and Recruitment (OR) Core, which reaches more than 2000 individuals annually. The OR Core supports and maintains Eligibility Database, which contains demographic and health information for all individuals who contact the ADC or are referred from clinic ( $n > 7000$ ,  $\sim 5000$  without cognitive complaints). Recruitment will also leverage the ADC Clinical Cohort, which is comprised of 400 individuals who are characterized annually with clinical and cognitive testing. The OR core has created a novel recruitment model, which consists of a centralized, dedicated team staffed by a lead recruitment coordinator and 4 recruitment specialists. This team supports recruitment and pre-screening. These efforts have improved enrollments and efficiency, receiving national attention as a novel model for approaching recruitment.[82]

### **B. Screening Interview/questionnaire: N/A**

### **C. Informed consent process and timing of obtaining of consent**

The consent form will be mailed to the participant at the time that they are scheduled for the study visit to allow adequate time for review prior to the visit. The participant will be given a phone number to reach the PI and study coordinator if they have any questions prior to the visit. The study coordinator and/or PI will go over the consent form in person the morning of the first study visit and answer any additional questions at that time. If a participant is deemed unable to provide consent for themselves by study staff, they will be excluded from the study.

### **D. Alternatives to Participation: N/A**

### **E. Costs to Subjects:** There is no cost to subjects for participation in this study.

### **F. How new information will be conveyed to the study subject and how it will be documented:** If they wish, we will provide the participant with their VO2 max score from the fitness test. No information regarding brain imaging will be conveyed to the subject.

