**B. Subject Criteria (See Vulnerable Populations appendix, if applicable):**

1. Inclusion criteria:
  - Age 60 and older
  - Stable medication doses (>1month)
  - Post-menopausal
  - Diagnosis of either Nondemented (CDR 0) or Probable AD (CDR 0.5 or 1 only)
2. Exclusion criteria:
  - Inability to provide consent
  - Diagnosis of insulin-dependent (Type 1) Diabetes Mellitus
  - Recent ischemic heart disease (<2 years)
  - Diagnosis of an clinically significant chronic disease including CVD, other metabolic diseases (e.g., thyroid), cancer, HIV, or acquired immunodeficiency syndrome
  - Excluded from or unable to complete an MRI scan
  - Any Neurological disorders that have the potential to impair cognition or brain metabolism (e.g., Parkinson's disease, stroke defined as a clinical episode with neuroimaging evidence in an appropriate area to explain the symptoms).
  - Clinically significant depressive symptoms that may impair cognition, abnormalities in B12, RPR, or thyroid function that may impair cognition, use of psychoactive and investigational medications, and significant visual or auditory impairment
3. Withdrawal/Termination criteria: If the participant has a serious AE during the maximal cardiorespiratory fitness test (Visit 1) we will not have the participant return for the rest of the study. Participants are allowed to participate in other observational studies during their enrollment period but not interventional trials.

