**E. Specific methods and techniques used throughout the study**

1. Laboratory tests:

A catheter will be placed to facilitate multiple blood draws. We will draw ~10cc of blood into an EDTA vacutainer tube at 6 timepoints throughout Visit 2 and Visit 3. Lactate levels will be analyzed immediately in whole blood using a Lactate Meter (Nova Biomedical). Blood will be processed for platelet rich plasma (PRP) and platelet free plasma (PFP) and will be stored for analysis. After initial analyses, remaining PRP and PFP will be stored in a locked freezer in [name] laboratory (2nd floor Hemenway, badge access area).

2. Study Procedures:

Diagnostic assessment (Visit 1): We will leverage established KU ADC criteria for diagnosing subjects as ND or AD. A clinician evaluates all participants with the Clinical Dementia Rating (CDR) [74, 75] and a standard physical and neurological examination using UDS 3.0 Forms and Scales. The UDS 3.0 neuropsychological test battery is then administered. Due to COVID-19, we will be administering the CDR and neuropsychological testing (T-Cog) by telephone to reduce the amount of time spent in the clinic during Visit 1.

To participate in the study, participants will meet criteria for etiologic diagnosis of probable AD (any age, CDR 0.5 or 1) or normal aging (ND, 60 years and older). All participants are required to have a study partner (someone who routinely interacts with participant > 5 times a week) to be available to speak with the clinician via telephone. The study partner will be consented over the phone and will not be required to accompany the participant to any visits. Their involvement in the clinical evaluation will be explained by study staff and will be allowed to ask questions. The study partner will be sent a form from REDCap to add

digital signature. Exclusion criteria include significant neurological disease other than AD that may affect cognition (e.g., stroke, major depression, etc.) history of cancer within the last 5 yrs (except non-metastatic basal or squamous cell carcinoma), history of drug/alcohol abuse (DSM-IV criteria) within the last 2 yrs, and visual or auditory limitations that will interfere with the cognitive assessments. Any available clinical imaging data is also reviewed for abnormalities that may explain cognitive complaints (such as multiple lacunar infarcts or a single infarct  $> 1 \text{ cm}^3$ , prior hemorrhage  $> 1 \text{ cm}^3$ , or evidence of structural damage).

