**Cardiorespiratory Fitness Testing (Visit 1):** Subjects will be tested for  $\text{VO}_2$  peak using a Bruce protocol on a treadmill as previously described [76]. Relative ( $\text{ml/kg}^{-1}/\text{min}^{-1}$ ) and absolute ( $\text{L/min}^{-1}$ )  $\text{VO}_2$  peak and treadmill time to exhaustion will be used as determinants of aerobic capacity. Our ADC has validated  $\text{VO}_2$  peak testing in AD patients [76, 77] and in older control adults [4] and currently uses the same assessment in 3 ongoing clinical exercise intervention trials. Subjects are attached to a 12-lead electrocardiograph and wear a non-rebreathing facemask to assess heart rate, blood pressure, and expired air (oxygen, carbon dioxide) using a Parvomedics system.  $\text{VO}_2$  peak is the highest observed value during the test[78, 79] and maximal effort is defined as meeting 3 of 4 criteria: a plateau in  $\text{O}_2$  consumption, a respiratory exchange ratio (RER)  $\geq 1.0$ , a maximal heart rate within 90% age-predicted maximum, or volitional fatigue.[80] If the medical monitor detects abnormalities during the ECG, physician's clearance will be required prior to PET scans. This form will be faxed to primary care or cardiologist with ECG and medical monitor's notes.

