**FDG-PET imaging:** FDG PET images will be obtained at a satellite location of the University of Kansas Hospital, the KU Cancer Center – Overland Park (KUCC-OP). The scanner is accredited by the American College of Radiology (ACR), and our physicists perform annual required testing by scanning an Esser PET phantom with 18F to assess SUV range, contrast resolution, spatial resolution, and uniformity. In addition to the ACR annual testing, the nuclear medicine department routinely performs quality control procedures on a daily, weekly, and quarterly basis. Frames are reconstructed to a single PET image in native space. Adverse events will be continuously monitored during the imaging session. The radiation dose from the two FDG PET scans will not exceed 2100 mrem. While this exceeds the amount obtained through normal background exposure, it is considered by Radiation Safety to be well below the risk levels acceptable in research and medical practice. PET images will be analyzed using custom software written for Statistical Parametric Mapping (SPM12). Pre- and post-intervention P images will be co-registered. A priori regions of interest masks from the Automated Anatomic Labeling series will be inverse warped to match native space images. The PET images will be standardized to the uptake value of the cerebellum and standardized uptake value ratios (SUVR) will be calculated from native-space ROIs as determined by MRI. Regional SUVR will be compared using paired t-tests or linear mixed models as appropriate.

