monitored during the warm up. Four minutes after the warmup begins (1 min prior to FDG injection), Draw 2 will be taken. Immediately following the 5 min warm up, FDG will be injected through the IV catheter that was placed prior to exercise. Following injection, participants will maintain cycling at either 45-55% or 65-75% of their HRR for 15 min. We will use an electronically-braked cycle ergometer (Lode, Groningen, Netherlands) to precisely control HR and workload. Rating of perceived exertion (RPE) will be collected every 2 minutes to assess effort. Participants will maintain a consistent pedaling rate (60-70 rpm) as this may affect physiological variables. [111] Immediately following the 15 min exercise at the target intensity, Draw 3 will be taken. At this time, the participant will begin a cool down period that lasts 5 min. Blood pressure will be monitored during the cooldown. The participant will dismount the bicycle and move to the scanner table. Draw 4 will be taken at 30 minutes before the scan. After the scan is complete a blood draw will be taken at minute 45 and a short cognitive performance test (NIH Toolbox Cognition Battery) will be performed. The final blood draw will be taken after the scan is complete, at minute 75. We will provide up to 120mL of water as needed to account for any dehydration that may affect blood volume during exercise. The amount of water consumed by each participant during exercise will be noted by the study coordinator.

Cognitive performance analyses (Visits 2 and 3): Most work assessing acute cognitive change following exercise has focused on executive function testing. We will administer a short battery of cognitive tests using the NIH Toolbox Cognition Battery on an iPad 5 minutes following the end of the FDG-PET scan at minute 50. These will assess executive function, attention, processing speed and episodic memory, given data linking these domains with exercise and physical activity.[1, 112] Different versions of these tests will be used between the resting and exercise visits where available.

MRI Scan (Visit 4): Structural MRI will use a Siemens 3.0 Tesla Skyra MRI scanner. We will obtain high resolution T1 weighted (MPRAGE) images following the ADNI2 standard. High-res T1 weighted anatomic images provide gross anatomy with high gray-white matter contrast (MP-RAGE; 1x1x1mm voxels; TR=2300, TE=2.98, TI=900, FOV, 1mm thickness, flip angle 9°). Neuroimages will be processed via Freesurfer. [81]

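### Section III.F rules out returning any brain-imaging information and, as worded, makes no exception for a suspected incidental abnormality that staff happen to notice

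*Combined protocol and SAP*

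**What the plan says.** Section III.F offers participants their fitness-test score if they want it, and then states: "No information regarding brain imaging will be conveyed to the subject". It attaches no condition. Section V.C, on study results to participants, again offers only the VO2 value and does not mention imaging.

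Each participant has two FDG PET scans (Visits 2 and 3, Section II.A), which the risk text in Section II.F describes as PET/CT, and one structural MRI at Visit 4. Section II.E describes these images as research measurements. PET is processed with custom software into regional uptake ratios. For MRI, "We will obtain high resolution T1 weighted (MPRAGE) images following the ADNI2 standard", followed by automated processing. No diagnostic read of either is described.

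Screening addresses known disease. Section II.B excludes "Any Neurological disorders that have the potential to impair cognition or brain metabolism", with stroke given as an example. Section II.E adds that "Any available clinical imaging data is also reviewed for abnormalities that may explain cognitive complaints".

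**The concern.** Section III.F is where study staff would look to learn what they may tell a participant, and its imaging rule is absolute. The participants are mostly aged 60 or older and are scanned three times. Suppose someone handling a scan sees what looks like a mass or a bleed. Followed to the letter, the sentence tells them to say nothing to the person concerned. At stake is a delay in care for a participant with an abnormality that staff had seen. No statistical quantity in the plan is involved.

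**Working it through.** The plan states no figure to reproduce. The check consists of a count of the scans that the rule covers and a comparison of the sections that might supply an exception.

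**Scans covered**

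- Inputs: two FDG PET scans and one MRI per participant (Sections II.A and II.E); 60 participants planned and 66 to be recruited (Section V.A, sample size justification).
- Sessions per participant: 2 + 1 = 3.
- For 60 participants: 60 × 3 = 180, made up of 120 PET/CT and 60 MRI.
- For 66 recruited: 66 × 3 = 198 at most, made up of 132 PET/CT and 66 MRI. Dropouts before Visit 4 would lower this.

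These counts show the reach of the sentence. Turning them into expected findings would need a prevalence and a chance of being noticed. The documents give neither, so no rate is offered.

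**Sections that might supply an exception**

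1. *Section V.C (study results to participants).* It covers only the VO2 value and justifies returning it because the value carries no clinical meaning. It is silent on a finding that does carry clinical meaning.
2. *Section II.E (diagnostic assessment).* The imaging review there concerns clinical images that already exist and serves diagnosis. It does not cover the study scans.
3. *Section II.E (fitness testing).* An abnormal ECG requires a physician's clearance before the PET visits: "This form will be faxed to primary care or cardiologist with ECG". This is a safety gate before exercise and does not deal with imaging findings.
4. *Section II.F (protection against risk).* Health information is withheld from outside parties and from the subject's "personal physician unless requested in writing by the subject after full disclosure of risks". This governs disclosure to third parties. It neither permits nor forbids telling the participant.
5. *Section II.I (safety monitoring).* It covers adverse events and reports to the monitoring committee. It has no step for informing a participant of something seen on a scan.

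None of the five qualifies III.F.

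**Whether the situation can arise**

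The exclusions depend on known diagnoses, and prior images are reviewed only where they exist. A new or unrecognised lesion could therefore first appear on a study scan. Section II.H places radiology staff, a nurse, the principal investigator and the coordinator at Visits 2 and 3, and an MRI technician at Visit 4. It lists who is present, not who interprets images. With no diagnostic read described, any abnormality would be noticed by chance.

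**The case against.** The strongest reply is that the sentence is a policy of not returning research results and was never meant to silence staff about a suspected tumour. Its place beside the optional VO2 score, and the parallel text in V.C, support that reading. I accept it as the probable intent. The remaining defect is that the written rule is broader than the intent.

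The second reply is that an exception may exist in text that could not be examined. The consent pages are missing, so is some text around the end of Section III, and the lettering in Section II runs from B to E. This stands as a real limit. However, III.F itself is complete on this point, and if the consent form does contain an exception, the two texts need to be reconciled.

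Third, harm requires several things in sequence: an abnormality is present, it was not known before, someone notices it by chance, and staff then apply the sentence literally. None of these steps can be quantified from the documents. This also stands, and it is why the point is minor.

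A reader might draw stronger conclusions that the documents do not support:

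- *That participants will be denied safety information.* The documents show only what literal application would do. They do not show that staff would apply the rule that way.
- *That the plan contradicts itself because ECG abnormalities have a route and imaging does not.* The ECG step is clearance before exercise and was not designed to return findings, so the difference is no inconsistency.
- *That Section II.F closes a second route to the participant.* It concerns third parties only.
- *That study scans must be read by a radiologist.* Nothing in the plan implies this, and the correction does not need it.

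**Conclusion.** The point holds as a minor participant-safety wording correction. III.F states an absolute rule, and no section available for review qualifies it. Taken literally, it would bar telling a participant about a suspected incidental abnormality that had been noticed. It reaches 180 imaging sessions, or at most 198, with no estimate of how many would show anything. The endpoint, sample size and analysis are unaffected.

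The conclusion rests on two assumptions: that the unavailable text contains no exception, and that staff might follow the sentence as written. If the consent form already has an exception, what remains is to bring III.F into line with it.

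**What to change.** Replace the imaging sentence in III.F with wording such as:

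> Research imaging results, including regional FDG uptake and any AD-like metabolic pattern, will not be returned. If staff happen to notice a suspected incidental abnormality that may need medical care (for example a mass, haemorrhage or infarct), it will be referred to a study physician designated by the PI, who will decide whether to inform the participant and, with the participant's written permission, their physician.

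Three features of this wording matter.

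- *It is narrow.* An open phrase about clinical significance could take in an Alzheimer-like FDG pattern in a nondemented participant, which would undo the policy of not returning research results.
- *It names an owner without presuming who is qualified.* The clinician who rates dementia at Visit 1 may seem a natural choice. That rating is now done by telephone, and nothing in the documents shows that this clinician sees the study scans or could judge them. The designation is better left to the principal investigator.
- *It fits Section II.F.* Written permission before the personal physician is contacted respects the existing restriction.

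Then check the consent form and align the two. The cost is a short amendment, a named physician, occasional false-alarm referrals, and some physician time to assess and document them. No visit and no routine diagnostic read is added.
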